- 23. Treatment with systemic corticosteroids (>10 mg daily prednisone equivalents) or other systemic immunosuppressive medications (including but not limited to prednisone, dexamethasone, cyclophosphamide, azathioprine, methotrexate, thalidomide, and anti-tumor necrosis factor [TNF] agents) within 2 weeks prior to start of study treatment, or requirement for systemic immunosuppressive medications during the trial. The use of inhaled corticosteroids and mineralocorticoids (e.g., fludrocortisone) is allowed.
 - a. Note: Patients who have received acute, low-dose, systemic immunosuppressant medications (e.g., a one-time dose of dexamethasone for nausea) may be enrolled in the study after discussion with and approval by the Sponsor.
- 24. Positive test for human immunodeficiency virus (HIV)
- 25. Active hepatitis B (defined as having a positive hepatitis B surface antigen [HBsAg] test prior to randomization) or hepatitis C.
 - a. Note: Patients with past hepatitis B virus (HBV) infection or resolved HBV infection (defined as having a negative HBsAg test and a positive antibody to hepatitis B core antigen antibody test) are eligible. Patients with detectable HBV-DNA are not eligible.
 - b. Note: Patients positive for hepatitis C virus (HCV) antibody are eligible only if polymerase chain reaction testing is negative for HCV ribonucleic acid (RNA).
- 26. Active tuberculosis.
- 27. Administration of a live, attenuated vaccine within 4 weeks prior to start of study treatment or anticipation that such a live attenuated vaccine will be required during the study.
- 28. Prior treatment with CD137 agonists, anti-CTLA4, anti-PD-1, or anti-PD-L1 therapeutic antibody or drug specifically targeting T-cell co-stimulation or immune checkpoint pathways, including prior therapy with anti-tumor vaccines.
- 29. Pregnancy or lactation. A serum pregnancy test is required within 7 days prior to start of study treatment, or within 14 days with a confirmatory urine pregnancy test within 7 days prior to start of study treatment

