- 23. Treatment with systemic corticosteroids (>10 mg daily prednisone equivalents) or other systemic immunosuppressive medications (including but not limited to prednisone, dexamethasone, cyclophosphamide, azathioprine, methotrexate, thalidomide, and anti-tumor necrosis factor [TNF] agents) within 2 weeks prior to start of study treatment, or requirement for systemic immunosuppressive medications during the trial. The use of inhaled corticosteroids and mineralocorticoids (e.g., fludrocortisone) is allowed.
 - a. Note: Patients who have received acute, low-dose, systemic immunosuppressant medications (e.g., a one-time dose of dexamethasone for nausea) may be enrolled in the study after discussion with and approval by the Sponsor.
- 24. Positive test for human immunodeficiency virus (HIV).
- 25. Active hepatitis B (defined as having a positive hepatitis B surface antigen [HBsAg] test prior to randomization) or hepatitis C.

- a. Note: Patients with past hepatitis B virus (HBV) infection or resolved HBV infection (defined as having a negative HBsAg test and a positive antibody to hepatitis B core antigen antibody test) are eligible. Patients with detectable HBV-DNA are not eligible.
- b. Note: Patients positive for hepatitis C virus (HCV) antibody are eligible only if polymerase chain reaction testing is negative for HCV ribonucleic acid (RNA).
- 26. Active tuberculosis.
- 27. Administration of a live, attenuated vaccine within 4 weeks prior to start of study treatment or anticipation that such a live attenuated vaccine will be required during the study.
- 28. Prior treatment with CD137 agonists, anti-CTLA4, anti-PD-1, or anti-PD-L1 therapeutic antibody or drug specifically targeting T-cell co-stimulation or immune checkpoint pathways, including prior therapy with anti-tumor vaccines.
- 29. Pregnancy or lactation. A serum pregnancy test is required within 7 days prior to start of study treatment, or within 14 days with a confirmatory urine pregnancy test within 7 days prior start of study treatment.

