- 30. For women who are not post-menopausal (< 12 months of non-therapy-induced amenorrhea) or surgically sterile (absence of ovaries and/or uterus): refusal to use a highly effective contraceptive method (i.e. with a failure rate of < 1% per year such as sexual abstinence, hormonal implants, combined oral contraceptives, vasectomized partner), during the study drug administration and for at least 6 months after the last dose of study medication. Periodic abstinence [e.g., calendar, ovulation, symptothermal, postovulation methods] and withdrawal are not acceptable methods of contraception. A combination of male condom with cap, diaphragm or sponge with spermicide (double barrier methods) is not considered a highly effective birth control method. Acceptable methods of contraception may include total abstinence in cases where the lifestyle of the patient ensures compliance. A vasectomized partner is a highly effective birth control method provided that partner is the sole sexual partner of the trial participant and that the vasectomized partner has received medical assessment of the surgical success.
- 31. For men: refusal to use a highly effective contraceptive method (i.e. with a failure rate of < 1 % per year such as vasectomy, sexual abstinence or female partner use of hormonal implants or combined oral contraceptives) during the study drug administration and for a period of at least 6 months after the last dose of study medication. Periodic abstinence [e.g., calendar, ovulation, symptothermal, post ovulation methods] and withdrawal are not acceptable methods of contraception. A combination of male condom with either, cap, diaphragm or sponge with spermicide (double barrier methods) is not considered highly effective, birth control methods. Acceptable methods of contraception may include total abstinence in cases where the lifestyle of the patient ensures compliance. A vasectomized trial participant is a highly effective birth control method provided that the trial participant has received medical assessment of the surgical success.

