7 STUDY ASSESSMENTS AND PROCEDURES

All the study assessments are described in the schedule of assessment (Appendix I). Protocol waivers or exemptions are not allowed. Adherence to the study design requirements, including those specified in the Schedule of Activities, is essential and required for study conduct.

All immediate safety concerns must be discussed with the Sponsor immediately upon occurrence or awareness to determine if the participant should continue or discontinue treatment.

All screening evaluations must be completed and reviewed to confirm that potential participants meet all eligibility criteria before treatment assignment/randomization. The investigator will maintain a screening log to record details of all participants screened and to confirm eligibility or record reasons for screening failure, as applicable.

Procedures conducted as part of the participant's routine clinical management (e.g., blood count) andobtained before signing of informed consent may be utilized for screening or baseline purposes provided the procedure meets the protocol-defined criteria and has been performed within the timeframe defined in the Schedule of Activities. Additional measures, including non-study required laboratory tests, should be performed as clinically indicated or to comply with local regulations. Laboratory toxicities (e.g., suspected drug induced liver enzyme evaluations) will be monitored during the follow-up phase via on site/local labs until all study drug related toxicities resolve, return to baseline, or are deemed irreversible.

If a participant shows pulmonary-related signs (hypoxia, fever) or symptoms (e.g. dyspnea, cough, fever) consistent with possible pulmonary adverse events, the participant should be immediately evaluated to rule out pulmonary toxicity, according to the suspected pulmonary toxicity management algorithm in the BMS- 936558 (nivolumab) Investigator's Brochure.

Some of the assessments referred to in this section may not be captured as data in the eCRF. They are intended to be used as safety monitoring by the treating physician. Additional testing or assessments may be performed as clinically necessary or where required by institutional or local regulations.

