7.7 Laboratory

7.7.1 Screening

- Hematology (CBC, hemoglobin, hematocrit, WBC count with differential [neutrophils, eosinophils, lymphocytes], and platelet count)
- Serum chemistry (glucose, BUN or urea, creatinine, sodium, potassium, calcium, total bilirubin, direct bilirubin, ALT, AST, ALP, Lactate Dehydrogenase [LDH], lipase and amylase,)
- CEA
- Serology (HIV, HBsAg, antibodies against HBsAg, total HBcAg antibody [anti-HBcAb], HCV antibody [anti-HCV]). HBV DNA should be obtained prior to randomization if patient has a negative serology for HBsAg and a positive serology for anti-HBcAb.
 - HCV RNA should be obtained prior to randomization if patient tests positive for anti-HCV
- Thyroid function testing (TSH, free T3, free T4)
- Serum pregnancy test within 14 days before Cycle 1 Day 1 for women of childbearing potential, including women who have had a tubal ligation.
 - A woman is not considered to be of childbearing potential if she is postmenarcheal, has not reached a postmenopausal state (defined as 12 continuous months of amenorrhea with no identified cause other than menopause), and has not undergone permanent surgical sterilization (removal of bilateral ovaries and/or uterus.
- Coagulation (INR and aPTT)

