- Tumor assessments will be done at screening and every 8 weeks (± 1 week) until disease progression per RECIST v1.1, or ir-RECIST, or loss of clinical benefit (patients who continue treatment after disease progression according to ir-RECIST), consent withdrawal, or death, whichever occurs first. After 12 months, patients will undergo tumor assessments every 12 weeks until confirmed disease progression. Patients who discontinue treatment for reasons other than disease progression (e.g., toxicity) will continue scheduled tumor assessments until disease progression, withdrawal of consent, or death, whichever occurs first. A CT (with contrast if not contraindicated) or MRI scan of the brain must be doneat screening to exclude CNS metastases. An MRI scan of the brain is required to confirm or refute the diagnosis of CNS metastases at baseline in the event of an equivocal scan.
- ^m All patients will be tested for HIV prior to the inclusion into the study and HIV-positive patients will be excluded from the clinical study. HBV serology will include HBsAg, antibodies against HBsAg, total HBcAg antibody (anti-HBcAb). HBV DNA should be obtained prior to the treatment phase if patient has a negative serology for HBsAg and a positive serology for anti-HBcAb. HCV serology will include HCV

- antibody (anti-HCV). HCV RNA should be obtained prior to the treatment phase if patient tests positive for anti-HCV.
- ⁿ Thyroid function testing includes TSH, free T3, free T4 and will be collected at screening and at every cycle of the second treatment phase.
- ^o Serum pregnancy test within 14 days before Cycle 1 Day 1 of the first treatment phase.
- ^p All Serious Adverse Events will be reported within 24 hours. All adverse events will be recorded until 30 days after the last dose of study treatment, and SAEs and AESIs will be recorded until 90 days after last dose of study treatment or initiation of new anti-cancer therapy, whichever occurs first. All other adverse events, regardless of relationship to study drug, will be reported until 30 days after the last dose of study drug or initiation of new anti-cancer therapy, whichever occurs first. After this period the investigator should report any serious adverse events or adverse events of special interest that are believed to be related to prior study drug.

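### Section 7.7.1 and Appendix I footnote o set a looser pregnancy-test rule than exclusion criterion 29, and Section 7.7.1 states the definition of childbearing potential the wrong way round

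*Protocol*

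**What the plan says.** The protocol states the timing of the pregnancy test in four places and in two versions.

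- **Exclusion criterion 29** (protocol summary and Section 4.2) gives two routes. The first is: "A serum pregnancy test is required within 7 days prior to start of study treatment". The second allows an older serum test with a backup: "or within 14 days with a confirmatory urine pregnancy test within 7 days" before treatment starts.
- **Section 7.7.1, Screening**, gives one route and no urine test: "Serum pregnancy test within 14 days before Cycle 1 Day 1 for women of childbearing potential". It adds that women with a tubal ligation are included.
- **Appendix I, footnote o**, gives the same single route: "Serum pregnancy test within 14 days before Cycle 1 Day 1 of the first treatment phase".

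The protocol also describes twice which women can conceive.

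- **Section 7.7.1**: "A woman is not considered to be of childbearing potential if she is postmenarcheal, has not reached a postmenopausal state", with a third condition that she has not been permanently sterilised by surgery.
- **Exclusion criterion 30** (protocol summary and Section 4.2) imposes highly effective contraception and opens: "For women who are not post-menopausal (< 12 months of non-therapy-induced amenorrhea) or surgically sterile".

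Section 7 sets the status of these texts. It requires adherence to the schedule, forbids waivers, and requires all eligibility criteria to be confirmed before treatment assignment. Section 7.2 repeats that confirmation as a condition of enrolment. For a routine procedure done before consent, Section 7 accepts the result if it meets the protocol's criteria and "has been performed within the timeframe defined in the Schedule of Activities".

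**The concern.** The schedule is what site staff work from, and Section 7 tells them that keeping to it is required. A site that does what footnote o says, and no more, can enter a woman whose only test is 8 to 14 days old. It will have followed the schedule and still broken an exclusion criterion, with no waiver available.

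The definition raises a separate problem. Section 7.7.1 limits testing to women of childbearing potential and then defines that group so as to leave out fertile women. Read literally, it drops the women for whom the test exists.

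What is at stake is eligibility compliance and consistent safety screening. The lead-in drug is an alkylating agent, Section 1.4.3.1 warns of a potential risk to pregnancy with nivolumab, and Section 6.1 makes pregnancy a reason to stop treatment. The primary endpoint, the sample size and the decision rule are not touched.

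**Working it through.** There is no stated figure to reproduce. The check compares texts and counts days. I take the start of study treatment to be the first temozolomide dose, that is Cycle 1 Day 1 of the first treatment phase, as footnote o does.

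**Step 1: the window.** Take a woman with one serum test and no urine test.

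| Day of the only serum test | Section 7.7.1 and footnote o | Criterion 29 |
|---|---|---|
| -7 to -1 | met | met (first route) |
| -14 to -8 | met | **not met**: too old for the first route, no urine test for the second |
| before -14 | not met | not met |

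Days on which the two rules disagree: 14 - 8 + 1 = 7. Share of the schedule's window: 7 / 14 = one half.

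The figure of 14 days is not itself the conflict, because criterion 29 also accepts a serum test of that age. The conflict is the missing urine confirmation in the last 7 days. Each version appears in two separate places, so this is not an artefact of reading one line from the PDF.

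**Step 2: the definition.** Take the three conditions in Section 7.7.1 together.

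| Condition | What it describes |
|---|---|
| has reached menarche | reproductive age has begun |
| has not reached a postmenopausal state | reproductive age has not ended |
| ovaries and uterus not surgically removed | no permanent sterilisation |

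A woman who meets all three can conceive, yet the sentence says she is not of childbearing potential. Criterion 30 uses the same two tests, menopause and surgical sterility, and puts the same women under mandatory contraception. It does not use the term childbearing potential, but the group is the same.

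The sentence also conflicts with the line above it in Section 7.7.1. A premenopausal woman with a tubal ligation keeps her ovaries and uterus, so she meets all three conditions. The first line orders a test for her and the next exempts her. Removing the negative resolves both conflicts.

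**Step 3: who is exposed.** The test is done at screening, so the rule applies on entry to the lead-in. The protocol summary and Section 4 plan about 100 patients there, of both sexes, and 27 in the combination phase. The relevant base is therefore the women of childbearing potential among about 100, not among 27. The protocol does not give their share, so I put no number on it.

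**The case against.** The strongest reply is that nothing unsafe is authorised. Every version can be satisfied at once: a serum test within 7 days, or one within 14 days plus a urine test within 7, meets all four texts. Sections 7 and 7.2 require every eligibility criterion to be confirmed, so criterion 29 prevails. The Section 7 sentence on routine tests asks for the protocol's criteria as well as the schedule's timeframe, and a lone serum test on day -14 to -8 fails the first of these. The inverted sentence is an evident slip beside the tubal-ligation line, and criterion 29 and footnote o carry no qualifier that would exempt anyone.

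All of that stands, and it rules out the stronger reading. A reader might infer that footnote o permits dosing without confirmation, or that fertile women would be treated untested. The document supports neither.

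It does not remove the defect. That two rules can both be met does not make them equal: one can be met while the other is broken, on half the days of the window. The shorter rule sits in the schedule that sites are told to follow.

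A reader might also infer an error from the single pregnancy-test mark in Appendix I, at screening, with nothing before the first nivolumab and ipilimumab dose. That contradicts no other text. The protocol relies on contraception during treatment and on extra testing when clinically indicated. A repeat test would be a preference about design, and I do not count it here.

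**Conclusion.** Both parts hold as contradictions within the protocol. Section 7.7.1 and footnote o are incomplete against criterion 29 on 7 of the 14 days they allow, when no urine test is done. Section 7.7.1 defines childbearing potential backwards against criterion 30 and against its own preceding line. These are operative safety-screening rules and should be corrected.

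The realistic consequence is an eligibility deviation, or inconsistent decisions between sites on whom to test. It falls on women of childbearing potential entering the lead-in. No efficacy result, power or error rate changes.

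I give no expected number of pregnancies. Criterion 30 defines an acceptable contraceptive method as one "with a failure rate of < 1% per year", and it is tempting to turn that into an upper bound. It would not be one: it assumes full adherence, and criterion 30 requires contraception only during and after drug administration, not on the days between the test and the first dose.

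The conclusion rests on two readings: that the start of study treatment is the first temozolomide dose, and that criterion 29 governs where the texts differ.

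**What to change.** 1. In Section 7.7.1 and Appendix I footnote o, replace the single 14-day window with criterion 29's rule: a serum test within the 7 days before the first temozolomide dose, or a serum test within 14 days together with a confirmatory urine test within 7 days.
2. In the Section 7.7.1 definition, delete the first negative, so that a woman who has reached menarche, is not postmenopausal and has not been surgically sterilised is of childbearing potential. This matches criterion 30 and the tubal-ligation line.

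The cost is amended wording in two places and one deleted word. Neither change adds a visit, a procedure beyond what criterion 29 already requires, or any statistical consequence.

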> 1% of subjects were: fatigue (1.6%), lymphopenia (1.3%), abdominal pain (1%), diarrhea (1%), hypophosphatemia (1%) and pneumonitis (1%). At least one SAE was reported for 150 (49.3%) of the 304 subjects at all dose levels. Grade 3-4 SAEs were reported for 23 subjects (7.6%). Drug-related SAEs occurred in 11.5% of subjects. Grade 3-4 drug-related SAEs reported in at least 2 subjects included diarrhea (3 subjects, 1.0%), pneumonitis (3 subjects, 1.0%), pneumonia (2 subjects, 0.7%) and lipase increased (2 subjects, 0.7%). Additional select treatment-related AEs have occurred with low frequency (< 5%) but are considered clinically meaningful, as they require greater vigilance for early recognition and prompt intervention. These AEs include: ALT increased (4.3%), AST increased (3.6%), pneumonitis (3.3%), hypothyroidism (3.0%), hyperthyroidism (1.3%), renal failure (1.0%), adrenal insufficiency (0.7%) and colitis (0.7%). Grade 3-4 events of pneumonitis were reported in 3 subjects (1.0%) as described above (1 event was Grade 4). Grade 3 events of colitis, ALT increased, and AST increased were reported in 2 subjects(0.7%) each. Grade 3 events of adrenal insufficiency, hyperthyroidism, and hypothyroidism were reported in 1 subject (0.3%) each. Treatment-related AEs leading to discontinuation were reported in 18 (5.9%) of the

304 treated subjects in CA209003. The only events reported in more than 1 subject were pneumonitis (4 subjects; 1.3%) and hepatitis (2 subjects; 0.7%). There were 3 (1%) drug related deaths; each occurred after development of pneumonitis. Preliminary new non-clinical safety findings of adverse pregnancy outcomes and infant losses in the absence of overt maternal toxicity have been reported. The findings of increased late stage pregnancy loss and early infant deaths/euthanasia in nivolumab exposed pregnant monkeys suggest a potential risk to human pregnancy if there is continued treatment with nivolumab during pregnancy.

Additional details on the safety profile of nivolumab, including results from other clinical studies, are also available in the Investigator's Brochure.

Nivolumab Combined with Ipilimumab

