6 TREATMENT DISCONTINUATION CRITERIA

6.1 Discontinuation from Study Treatment

Patients must discontinue study treatment if they experience any of the following:

- Symptomatic deterioration (i.e., uncontrollable pain secondary to disease or unmanageable ascites, etc.) attributed to disease progression as determined by the investigator after integrated assessment of radiographic data, biopsy results, and clinical status
- Intolerable toxicity related to TMZ, NIVO and IPI including development of an immune-mediated adverse event determined by the investigator to be unacceptable given the individual patient's potential response to therapy and severity of the event
- Any medical condition that may jeopardize the patient's safety if he or she continues on study treatment
- Use of another non-protocol anti-cancer therapy
- Pregnancy

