7.7.2 Study treatment period

- Hematology (CBC, hemoglobin, hematocrit, WBC count with differential [neutrophils, eosinophils, lymphocytes], and platelet count) will be performed before treatment administration
- Serum chemistry (glucose, BUN or urea, creatinine, sodium, potassium, calcium, total bilirubin, direct bilirubin, ALT, AST, ALP, LDH, lipase, amylase, and LDH) will be collected before treatment administration
- Thyroid function testing includes TSH, free T3, free T4 and it will be collected at Day 1 of every cycle during the second treatment phase.
- CEA will be done every 8 weeks (± 1 week) of the second treatment phase until disease progression leading to treatment discontinuation. After 12 months of treatment, it will be performed every 12 weeks.

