8.7 Pregnancy

A pregnancy report will automatically be generated and sent to Safety Risk Management. Pregnancy should not be recorded on the Adverse Event eCRF.

Pregnancies must be reported and submitted to BMS. BMS will perform due diligence follow-up using the BMS Pregnancy Form which the investigator must complete.

The investigator should discontinue study drug and counsel the patient, discussing the risks of the pregnancy and the possible effects on the fetus. Monitoring of the patient should continue until conclusion of the pregnancy. Any serious adverse events associated with the pregnancy (e.g., an event in the fetus, an event in the mother during or after the pregnancy, or a congenital anomaly/birth defect in the child) should be reported on the Adverse Event eCRF.

If, following initiation of the investigational product, it is subsequently discovered that a study participant is pregnant or may have been pregnant at the time of investigational product exposure, including during at least 5 half-lives after product administration, the investigational product will be permanently discontinued in an appropriate manner.

The investigator must immediately notify the Sponsor in accordance with SAE reporting procedures.

Protocol-required procedures for study discontinuation and follow-up must be performed on the participant.

Follow-up information regarding the course of the pregnancy, including perinatal and neonatal outcome and, where applicable, offspring information must be reported to the Sponsor via EDC. Any pregnancy that occurs in a female partner of a male study participant should be reported to the Sponsor. Information on this pregnancy will be collected on the Pregnancy Surveillance Form. In order for Sponsor or designee to collect any pregnancy surveillance information from the female partner, the female partner must sign an informed consent form for disclosure of this information.

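### No pregnancy test is required before the first nivolumab/ipilimumab dose, when the last compliant test is about two months old; the screening text for that test also has two wording faults

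*Protocol*

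**What the plan says.** **When the test is done.** Footnote o of Appendix I reads "Serum pregnancy test within 14 days before Cycle 1 Day 1 of the first treatment phase", and the pregnancy row of the table carries a single mark, at screening. Section 7.7.1, which covers screening only, asks for "Serum pregnancy test within 14 days before Cycle 1 Day 1 for women of childbearing potential". Exclusion 29 in section 4.2 is stricter: "A serum pregnancy test is required within 7 days prior to start of study treatment, or within 14 days with a confirmatory urine" test within 7 days. Start of study treatment is the first lead-in dose of temozolomide.

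**What is tested later.** Section 7.7.2 lists haematology, chemistry, thyroid function and CEA for the treatment period, and no pregnancy test. For thyroid function it says that "it will be collected at Day 1 of every cycle during the second treatment phase", so new laboratory work was planned for the combination phase.

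**What the protocol says about pregnancy.** Section 1.4.3.1 reports animal findings with nivolumab that "suggest a potential risk to human pregnancy if there is continued treatment with nivolumab during pregnancy". Section 6.1 lists pregnancy under "Patients must discontinue study treatment if they experience any of the following". Section 8.7 adds that once a pregnancy is found, "the investigational product will be permanently discontinued in an appropriate manner".

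**Who counts as of childbearing potential.** Section 7.7.1: "A woman is not considered to be of childbearing potential if she is postmenarcheal, has not reached a postmenopausal state", and has not been permanently sterilised.

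**The concern.** The trial has two treatment starts. The first is temozolomide alone; the second, two cycles later, adds two new drugs, for one of which the protocol states a pregnancy risk. The test is attached to the first start only. A woman who becomes pregnant after the screening test can therefore begin nivolumab and ipilimumab, and stay on them, with no scheduled check that would bring the stopping rule of 6.1 and 8.7 into play. A site that follows the schedule to the letter would not be at fault.

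Two wording faults bear on the same test. The definition in 7.7.1 says that a woman is not of childbearing potential in exactly the circumstances in which she is, and it conflicts with exclusion 30, which describes the relevant women correctly. In addition, 7.7.1 and footnote o accept a serum test within 14 days with nothing further, so a site that uses the schedule as its checklist could breach exclusion 29.

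What is at stake is participant safety and consistent eligibility wording. The sample size, the error rates and the primary endpoint are not affected.

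**Working it through.** The protocol states no figure for the age of the test at the second start, so there is none to reproduce. The interval follows from its own timings.

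**Inputs**
- Lead-in: two 4-week cycles (section 5.2), so 2 × 28 = 56 days from lead-in Day 1 to second-phase Day 1, which is study day 57.
- Last compliant test: no more than 7 days before lead-in Day 1 under either route of exclusion 29, and at least 1 day before it, because the Appendix I screening window ends at day −1.
- Dosing window: ±3 days (Appendix I, footnotes u and w).
- Contraceptive failure rate: under 1% per year (exclusion 30).

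**Age of the test at the first nivolumab/ipilimumab dose** = days from test to lead-in Day 1 + days from lead-in Day 1 to the first combination dose.
- Nominal: 1 + 56 = 57 to 7 + 56 = 63 days.
- With the dosing window: 1 + 53 = 54 to 7 + 59 = 66 days.
- A dose delay in the lead-in adds to either range.

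**Chance of a new pregnancy over that interval**, per woman, taking the failure rate as constant and adherence as full: p < 0.01 × days / 365.
- 54 days: 0.01 × 54/365 = 0.148%.
- 66 days: 0.01 × 66/365 = 0.181%.

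**At least one among n women**, 1 − (1 − p)^n. The documents do not say how many of the 27 combination-phase patients would be women of childbearing potential, so n is an assumption:

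| n (assumed) | upper bound at 54 days | upper bound at 66 days |
|---|---|---|
| 1 | 0.15% | 0.18% |
| 5 | 0.74% | 0.90% |
| 10 | 1.47% | 1.79% |

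**Is there really only one test?** The Appendix I table is damaged in the text read from the PDF, so its single mark should not carry the argument alone. Three other places agree with it: footnote o names the first treatment phase, 7.7.1 sits under screening, and 7.7.2 has no such test.

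**The definition.** Section 7.7.1 lists three conditions: past menarche, not postmenopausal, not permanently sterilised. Together they describe a woman who can become pregnant. Exclusion 30 applies its contraception duty to women who are neither postmenopausal nor surgically sterile, which is the same group. The two agree once the negation in 7.7.1 is removed.

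**The case against.** The best case for the protocol is that this is a preference about testing frequency. Section 8.7 acts when a pregnancy is discovered and does not presuppose scheduled tests. Section 7 tells sites to add tests when clinically indicated or when local rules require them. Exclusion 30 and section 5.6.1 call for highly effective contraception. One extra test also leaves lead-in cycle 2 and every later combination cycle untested. All of this is fair, and it keeps the point minor. It does not remove it: testing on indication depends on suspicion, and the start of two new drugs is a natural decision point at which a check costs little.

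Three stronger readings are tempting and are not supported.
- A reader might infer from the 14-day wording of 7.7.1 and footnote o that the test can be 14 + 56 = 70 days old. Exclusion 29 binds every enrolled woman, and section 7 allows no waivers. That figure arises only at a site that ignores an exclusion criterion. The looser texts can be met together with the stricter one.
- A reader might infer that contraception is not required between the test and the first temozolomide dose, because exclusion 30 speaks of the period of drug administration. Section 5.6.1 asks for highly effective contraception without that time limit.
- A reader might infer that the inverted definition exempts fertile women from testing. Exclusion 29 requires the test without relying on that definition, so the women concerned are still reached. The sentence is wrong in operative safety text, but its practical effect is limited.

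**Conclusion.** The point holds in a limited form. No pregnancy test is required before the first nivolumab/ipilimumab dose, and the last compliant one is then nominally 57 to 63 days old (54 to 66 with the dosing window, more after a delay). This sits poorly with the protocol's own warning about nivolumab and its mandatory stop for pregnancy. The definition in 7.7.1 is wrong as written, and the windows in 7.7.1 and footnote o are looser than exclusion 29.

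The absolute risk is below about 0.2% per woman. That bound rests on a constant failure rate under 1% per year and full adherence to contraception; poorer adherence would raise it. The figures for several women rest on assumed numbers. The change is optional and low in priority, justified by a serious possible harm and a very cheap remedy.

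**What to change.** 1. In section 7.7.2 and in Appendix I (second-phase Cycle 1 column and footnote o), require a negative serum or urine pregnancy test within 7 days before the first nivolumab/ipilimumab dose in women of childbearing potential. The last test would then be at most 7 days old. If a positive result is confirmed, the two antibodies are not started and temozolomide stops, as 6.1 and 8.7 already require.
2. In section 7.7.1, delete the negation so that the sentence says who is of childbearing potential.
3. Align the screening window in 7.7.1 and footnote o with exclusion 29.

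The cost is one inexpensive test per eligible woman. A serum test can use the blood already drawn within 48 hours before dosing (Appendix I, footnotes h and j), so no extra visit is needed. A positive result needs confirmation and could delay the first dose briefly. Pregnancies that begin later would still depend on clinically indicated testing. The sample size, endpoint and analysis set stay as they are.
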